### **Analyses for Exploratory Aims**

Aim 1. Volume of breast milk at discharge will be compared via one-way ANOVA; weekly percentage of breast milk during hospitalization will be compared between the three groups using chi-square tests.

Aim 2. In a first step, unadjusted mean time to lactogenesis stage II and mean volume of breast milk over the first 6 weeks (days 1 through 42) will be compared between the four groups: early timing of initiation of expression (TIE) / 23-27 weeks of gestation, late TIE / 23-27 weeks of gestation, early TIE / 28-32 weeks of gestation, and late TIE / 28-32 weeks of gestation, using one-way ANOVA. Subsequently, post hoc pooled t-tests (Tukey's) will be used to compare time to lactogenesis stage II and volume of breast milk means pairwise for the two early and the two late TIE groups between the two degrees of prematurity (23-27 vs. 28-32 weeks) and for the early-late TIE groups within each degree of prematurity. Adjusted means will be obtained and compared between the groups using a general linear models (GLM) approach with gestational age/degree of prematurity group as the primary independent variable and time to lactogenesis stage II (or amount of breast milk expressed at days 1-7) as the dependent variable. Additional covariates will be included in the models to adjust for putative predictive variables as described above.

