### Sample Size Determination / Power Analysis

The primary foci of this study are amount of breast milk expressed after initiation and time to lactogenesis II. For the continuous longitudinal outcome amount of breast milk expressed, with 60 subjects randomized to each intervention group (early, intermediate, late initiation), we will have 85% power to detect at least a 0.5 standardized (sd units) effect size between the three intervention groups [assuming 13 time points (initial expression, days 1-7, 14, 21, 28, 35, 42)]; intra-class correlation no greater than 0.5; level of significance ( $\alpha$ )=0.02, two-tailed ]. A standardized effect size of 0.49sd (Cohen's d, "moderate" effect) is equivalent to a raw effect size of 125 ml (raw scale units) for expressed breast milk (assuming pooled sd for expressed breast milk is 250, from preliminary data. For number of hours to achieve lactogenesis II assuming  $\alpha$  = 0.02 (Type I error rate), two-sided; independent sample t-test comparison of means (adjusted for multiple comparison between 3 groups); equality of variance between groups with 60 mothers per group we will have 85% power to detect a difference of 34.1 hours (effect size  $\Delta$ =0.62s;  $s$ =55.0) between the groups.

For analysis of the continuous secondary efficacy outcome measure self-efficacy, we will have 85% power to detect a difference of 0.62 s between the three groups assuming  $\alpha$  = 0.02 (Type I error rate), two sided; independent sample t-test comparison of means; equality of variance between groups accounting for multiple comparisons.

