**Table 2. Instruments (Logs)**

Variable	Instrument	Measurement
Maternal Factors	Log maintained by Project Coordinator	Age, parity, diabetes, pregnancy induced hypertension, mode of delivery, type of anesthesia, experience with breastfeeding, smoking, obesity, antenatal steroids
Lactation Factors (1-3 below)		
1. Onset of lactogenesis stage II	Log maintained by Project Coordinator	Date and time of sensation of breast fullness Corresponding breast milk measurement
2. Milk volume	Log maintained by Project Coordinator	Daily total breast milk weight for days 1-7 24 hour sample weekly
3. Milk volume alternative for breastfed infants	Log maintained by Project Coordinator	(Test weighing) - difference in infant's weight before and after feeding as indicator of breast milk intake.
Behavioral Factors	Log maintained only by mother	Date and time of pumping sessions, episodes of lactation support. Kangaroo Care log will be maintained separately (see below).
Kangaroo care	Log maintained by nurse or mother	Incidence and length of kangaroo care in min.
Infant breast milk intake (1-2		

below)		
1. Weekly percentage of breast milk received by infant during first 6 weeks of life	Log maintained by Project Coordinator	Data extracted from medical record
2. Percentage of breast milk feedings at discharge	Log maintained by Project Coordinator	Data extracted from medical record

Mothers in all groups will be instructed to record daily in the Maternal Behavioral Factors log book the following data: number of expression sessions per day, the date and time of each pumping session, and whether they received lactation assistance (Appendix F). The frequency of milk expression will be verified by the research coordinator by documentation of the date and time of each vial of milk brought to the NICU. Kangaroo care is encouraged in this NICU and nursing protocols have been established to provide support to all mothers regarding provision of kangaroo care. Infants are also encouraged to suckle at the breast during kangaroo care. Episodes and duration of kangaroo care between mother and infant will be recorded on the Kangaroo Care log sheet (Appendix G) located at the infant's bedside by either the mother or the nurse. While control of these variables within the study is impossible, we will carefully document these behavioral factors to allow for inclusion in statistical analysis as adjustment variables.

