Prior to discharge it will be determined whether mothers are continuing to express breast milk. This will be determined by whether mothers are bringing expressed breast milk to the NICU for infant consumption. If they are no longer expressing breast milk, they will be contacted to determine whether they would be willing to participate in a 10 minute interview concerning reasons for cessation of breast milk expression and their feeling concerning cessation of lactation. If interested, an appointment will be made for the interview during a time when the mother will be present in the hospital visiting her infant and a ~~RA who is a~~ licensed registered nurse will ask the mother (5) questions (see addendum S). Should the mother find this to be a stressful topic, the interview will cease immediately and a social worker employed in the neonatal intensive care unit experienced with caring for mothers of premature infants will be immediately notified and will assess whether further services are required.

The percentage of breast milk the infant receives weekly and the percentage of breast milk the infant is receiving upon discharge (mL/kg/d for the week prior to discharge) will be collected from the medical records (Appendix J). Neonatal nurses and physicians caring for the infants will not be told of the mother's assigned group.

## Exploratory Aim 1

Exploratory Aim 1 is to examine the effect of timing of initiation of breast milk expression on infant breast milk intake (e.g., weekly percentage of breast milk the infant receives during hospitalization and amount of breast milk infant is being fed at discharge). This information will be collected from the infant's medical records.

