#### Design/Analysis Issues.

Analysis sets. For primary analyses the intent-to-treat (ITT) sample will be used comprising all randomized mothers patients. Secondary per-protocol (completer) analysis will include mothers who were compliant with protocol requirements and for whom all required measurements have been made. ITT and per-protocol analyses will be compared to test the sensitivity of our conclusions to non-adherence/attrition.

Missing data. Every attempt will be made by the study coordinator to keep mothers in the study, with the help of the student research team members and to obtain required measurements in order to ensure the completeness of the study data. To minimize potential bias due to missing observations, mothers will be contacted by phone if vials of expressed breast milk are missed, and reasons for missing data will be carefully documented. Subject participation will only be terminated due to safety reasons for mother and infant, withdrawal of consent, or loss to follow-up. Several approaches to handle missing data in the ITT analysis set will be employed. For continuous variables using a single end-of-study value (e.g., amount of milk expressed at day 42), Little and Rubin's multiple imputation methods will be used (Little & Rubin, 1997). For analyses of longitudinal outcome data, we will use longitudinal methods (e.g. mixed models) capable of dealing with missing data (Hedeker & Gibbons, 2006).

Multiple outcome variables. In order to address possible Type I errors due to the number of outcome variables, we specify the primary outcome measures a priori corresponding to the stated a priori hypothesis and maintain the alpha (significance) level at 0.02. For analysis of secondary outcome variables, we will further adjust resulting p-values using Bonferroni-type corrections for multiple outcomes. Both unadjusted and adjusted p-values will be reported.

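### Weekly breast milk percentage is a repeated, continuous infant measure, but Exploratory Aim 1 assigns it chi-square tests with no week term, contrary to the plan's own rule for longitudinal outcomes

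*Combined protocol and SAP*

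**What the plan says.** Analyses for Exploratory Aims, Aim 1, gives one method for this outcome: "weekly percentage of breast milk during hospitalization will be compared between the three groups using chi-square tests". It does not say how the percentage is categorised, whether weeks are tested one at a time or together, or how repeated values on one infant are handled.

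Table 2 lists the outcome as "Weekly percentage of breast milk received by infant during first 6 weeks of life". The Exploratory Aim 1 section describes it as "weekly percentage of breast milk the infant receives during hospitalization". So each infant contributes one value per week, up to about six over the first six weeks and fewer if discharged sooner.

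Design/Analysis Issues, in the paragraph on missing data, gives a general rule: "For analyses of longitudinal outcome data, we will use longitudinal methods (e.g. mixed models) capable of dealing with missing data". Analyses for Aim 1 follows that rule for expressed milk volume, with a mixed model containing arm, time, arm-by-time and gestational group. The exploratory section does not carry the rule over to infant intake.

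**The concern.** Two sections give different instructions for the same kind of data. The general rule calls for a longitudinal method. The outcome-specific sentence names a test for independent counts, and an analyst will normally follow the outcome-specific sentence.

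That sentence can be carried out in two ways. With one chi-square per week, the aim receives as many answers as there are weeks, each ignoring the others, with no rule for combining them. With all infant-weeks in one table, the same infant is counted several times as if independent.

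At stake is whether the timing of first expression changes what infants receive in hospital. Expected Outcomes predicts more breast milk in hospital for Group 1 infants, so a false or scattered result here would bear on a stated prediction.

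**Working it through.** **Inputs from the documents.** Sample Size Determination gives "with 60 subjects randomized to each intervention group", a two-sided alpha of 0.02, and an intra-class correlation (ICC) of at most 0.5 for milk volume. The 0.02 level is set for the primary outcomes ("maintain the alpha (significance) level at 0.02"). No level is set for exploratory aims, so results are shown at 5% and 2%.

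**The plan's own figure.** No power is stated for weekly percentage. The nearest statement is the one for lactogenesis II, 34.1 hours with SD 55.0:

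- 34.1 / 55.0 = 0.62.
- 0.62 × √(60/2) = 3.396. Subtracting the 0.02 two-sided critical value, 2.326, leaves 1.070, for a power of 85.8% (84.9% with the t distribution).

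The stated 85% is reproduced. This confirms the arm size and alpha, but says nothing about weekly percentage.

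**Assumptions, not in the documents.** Six complete weeks; one infant per mother; equal correlation between weeks, with the milk-volume ICC of 0.5 borrowed for infant intake; a normal scale cut near the median to form the chi-square table; and a gap of 0.5 SD between early and late arms in every week, with the intermediate arm halfway.

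**All weeks in one comparison.** The variance of an infant's six-week mean is (1 + 5 × 0.5)/6 = 0.583 of the single-week variance. Arm means of 0.5, 0.25 and 0 deviate from their average by 0.25, 0 and −0.25, so the non-centrality is 60 × (0.0625 + 0.0625)/0.583 = 12.9, giving about 90% power at 5%. For one week on the continuous scale it is 60 × 0.125 = 7.5, giving about 68%.

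**Weeks tested separately.** If the six tests were independent, the chance of at least one false positive would be 1 − 0.95^6 = 26% at 5% and 1 − 0.98^6 = 11% at 2%. Correlation between weeks lowers this slightly.

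**Infant-weeks pooled.** Under a median cut, an ICC of 0.5 becomes (2/π) × arcsin(0.5) = 0.333 on the binary scale. The design effect is 1 + 5 × 0.333 = 2.67. With 2 degrees of freedom the rejection rate is exp(−(critical value/2)/design effect):

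- At 5%: exp(−2.996/2.67) = 33%.
- At 2%: exp(−3.912/2.67) = 23%.

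If 0.5 is instead taken directly on the binary scale, the design effect is 3.5 and the rates are 42% and 33%.

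**Simulation under the same assumptions:**

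| Analysis | False positive, 5% | False positive, 2% | Power, 5% | Power, 2% |
|---|---|---|---|---|
| One week, chi-square | 5% | 2% | 48% | 33% |
| Six weekly chi-squares, any significant, uncorrected | 23–25% | 10% | – | – |
| Six weekly chi-squares, Bonferroni | 5% | 2% | 64–67% | 48% |
| Infant-weeks pooled, one chi-square | 33% | 23% | – | – |
| Infant's six-week mean, one ANOVA | 5% | 2% | 90% | 82% |

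Power is omitted where the error rate is not controlled. The 64–67% spread reflects simulation error and where the cut is placed. The ANOVA on infant means stands in for the week-averaged contrast of a mixed model with complete data.

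**Sensitivity.** Over ICC 0.05 to 0.8, the pooled false-positive rate at 5% runs from about 7% to 49%. All-weeks power at 5% is about 98% at ICC 0.3 and 75% at ICC 0.8.

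**Separating out dichotomisation.** With the median split kept but all weeks used and the infant as the unit, power at 5% is 83%. Of the 23 points between 67% and 90%, about 16 (83 − 67) then come from splitting by week and 7 (90 − 83) from dichotomising. The split depends on the order in which the two are removed.

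**The case against.** The strongest reply is that the sentence speaks of a weekly percentage and of tests in the plural, and that the unadjusted milk-volume comparison in Analyses for Aim 1 also covers separate days. On that reading each weekly test is valid. This stands. A reader might infer that the plan commits to an analysis with a one-in-three false-positive rate, but no section says that infant-weeks will be pooled. The 33% applies only to a reading that the text leaves open.

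Second, Design/Analysis Issues promises Bonferroni-type correction beyond the primary outcomes, and correcting over six weeks restores the level. This stands in part: the rule names secondary outcomes, and does not clearly reach weeks within one exploratory outcome.

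Third, a reader might set 48% for one week against 90% for all weeks. That is not like for like, because it compares one dichotomised week with six continuous ones. The fairer comparison is 67% against 90%, and part of that is still dichotomising.

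Fourth, a reader might infer that chi-square cannot cope with early discharge, or that every infant supplies at least six values. Neither is supported. A weekly test simply uses the infants still in hospital, and the documents set no minimum number of weeks. Nor is this the only information on in-hospital intake: the discharge measure, compared by ANOVA, draws on the week before discharge.

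Finally, the general rule on longitudinal data already permits the better analysis. It does, but it does not override a test named for this outcome, so the two sections still have to be reconciled.

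**Conclusion.** The concern holds for this exploratory analysis. The named test does not fit a continuous measure repeated on each infant, and it conflicts with the plan's general rule and with its handling of maternal milk volume.

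Under the week-by-week reading, the cost is several separate answers instead of one, with either an uncontrolled error rate across weeks or a moderate loss of power after correction. Under the pooled reading, the cost is a seriously inflated error rate.

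The sizes rest on the borrowed ICC, six complete weeks, a median cut and an effect sustained over all weeks. The ICC of 0.5 is the plan's upper bound for a different outcome. Pooling inflates error for any positive correlation; the power loss from splitting would differ if the effect were confined to a few weeks. A reader might take this as a threat to the main findings, but milk volume and lactogenesis II have their own analyses, and no stated sample size or power figure depends on this test.

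**What to change.** In Analyses for Exploratory Aims, Aim 1, replace the chi-square sentence for weekly percentage with one longitudinal model on the continuous percentage:

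- **Model:** a linear mixed model, or a GEE with robust standard errors because the percentage is bounded at 0 and 100.
- **Terms:** arm, week, arm-by-week and gestational stratum.
- **Correlation:** repeated weeks within infant, and clustering on the mother, since twins are included.
- **Data:** weeks in hospital only, over the first six weeks, so that the windows in Table 2 and the Exploratory Aim 1 section agree.
- **Test:** the week-averaged comparison of the three arms as the single test of this outcome, with its significance level stated. Weekly percentages by arm remain as description.

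The cost is a short change of wording and a type of model that the team already plans to fit; no new data are needed. There are two downsides. A bounded outcome needs robust errors. Discharge ends in-hospital intake and is not ordinary missing data, so averaging over six weeks requires a stated restriction to, or an explicit assumption about, infants who leave earlier.

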### Randomization

Table 1. Randomization and Stratification of Mothers

Gestational Age	Group 1 Early Expressers	Group 2 Intermediate Expressers	Group 3 Late Expressers
23-27 weeks	0-60 minutes	61-180 minutes	181-360 minutes
28-32 weeks	0-60 minutes	61-180 minutes	181-360 minutes

mothers into groups. Following the birth of an infant weighing less than 1500 grams, with a gestational age between 23-32 weeks, mothers who continue to meet inclusion criteria will be stratified according to the gestational age of the infant (23-27 weeks and 28-32 weeks). Gestational age will be determined through one of the following; 1st or 2nd trimester ultrasound or the average of the obstetric gestational age and the results of the Ballard exam. This stratification is based upon likely differences in breast milk production in mothers who deliver earlier in gestation due to decreased mammary gland development and decreased levels of prenatal hormones necessary for preparation of the breast for lactation.

Following stratification, mothers will be randomly assigned to one of three groups to begin milk expression at different time periods following delivery. Group 1 (early expressers) will begin milk expression 0-60 minutes following delivery, Group II (intermediate expressers) will begin 61-180 minutes following delivery, and Group III (late expressers) will begin 181-360 minutes following delivery. The selection of the time periods for the groups is based upon our preliminary data showing greater milk volume and earlier lactogenesis stage II in women who began milk expression within 1 hour following delivery compared to those who began milk expression 1-6 hours following delivery (Parker et al., in press).

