### **Exploratory Aim 2**

Exploratory Aim 2 is to examine the effect of timing of initiation of breast milk expression on milk volume and lactogenesis stage II in mothers who deliver at an earlier gestation (23-27 weeks) and those who delivery at a later gestation (28-32 weeks). Information will be collected according to the procedure in Aim 1.

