### **Analyses for Aim 1**

The primary efficacy outcomes are amounts of breast milk expressed over the first 7 days post-initiation; days 14, 21, 28, 35, and 42 days post-initiation and weekly, and number of days to achieve lactogenesis stage II. To examine expressed breast milk amount over time (i.e. production of breast milk immediately after initiation and subsequently, volume measured daily over the first 7 days and on days 14, 21, 28, 28, and 42 post-initiation and weekly), we will compare the longitudinal profile of milk volume expressed in the three groups over the

study period using mixed effects models (MEM) analyses. These analyses will estimate the average change in breast milk volume within each group (early vs. immediate vs. late initiation) and individual change in breast milk volume for each mother. MEM analyses allow for missing data, measurement of study subjects at different time points during the study, and time varying covariates. MEM can also take into account the effect of clustering, i.e. correlation of repeated breast milk measurements within one subject (Hedeker & Gibbons, 2006; McCulloch & Searle, 2001). The efficacy variable expressed breast milk volume (mL) will be used as the dependent variable with treatment status (early vs. intermediate vs. late initiation), time and time-by-treatment interaction and gestational group (23-27 weeks vs. 38-32 weeks) as primary independent variables. In a second step, additional covariates will be included in the models to adjust for putative predictive variables such as age, mother's weight at delivery, diagnosis of preeclampsia or diabetes, parity, birth weight, weeks of gestation, behavioral factors including skin-to-skin contact ("kangaroo care"), lactation support and mean number of pumping attempts per day. Effect modifications of covariates will be examined through inclusion of a covariate-by-treatment interaction term in the multivariable models. For example, a significant age-by-treatment interaction would suggest that the relationship between treatment and milk volume is different for older mothers compared to younger mothers. Potential key intervening variables such as behavioral factors will be further examined using mediation analysis. Further, the relationship of maternal mood with amount of breast milk will be examined by inclusion of the MAACL-R scores obtained at discharge, days 21 and 42 in the longitudinal MEM model.

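### Exploratory Aim 2's ANOVA and Tukey steps leave out the intermediate arm without a reason, and Exploratory Aim 1 applies chi-square to a weekly percentage with no categories defined (minor)

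*Combined protocol and SAP*

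**What the plan says.** **Design and objective.** The Randomization section defines two gestational strata (23-27 and 28-32 weeks) and three timing arms: "Following stratification, mothers will be randomly assigned to one of three groups". Exploratory Aim 2 is to "examine the effect of timing of initiation of breast milk expression on milk volume and lactogenesis stage II in mothers" of earlier and of later gestation. It excludes no arm.

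**Planned analysis of Exploratory Aim 2** (Analyses for Exploratory Aims):

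- Unadjusted mean time to lactogenesis II and mean volume over days 1-42 "will be compared between the four groups: early timing of initiation of expression (TIE"). The list then names early and late cells in each stratum and nothing else.
- Tukey comparisons follow, for same-timing cells between strata and "for the early-late TIE groups within each degree of prematurity".
- An adjusted step comes last: "Adjusted means will be obtained and compared between the groups". The plan describes the model for this step as follows: "using a general linear models (GLM) approach with gestational age/degree of prematurity group as the primary independent variable". The outcome is time to lactogenesis II ("or amount of breast milk expressed at days 1-7) as the dependent variable").

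**Planned analysis of Exploratory Aim 1** (same section). Weekly percentage of breast milk is compared across the three arms by chi-square. The opening Statistical Analysis paragraph assigns chi-square to categorical variables. Table 2 describes the measure as a weekly percentage taken from the medical record and gives no cut-offs.

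**Related models.** Analyses for Aim 1 specifies a three-arm mixed model with treatment, "time and time-by-treatment interaction and gestational group (23-27 weeks vs. 38-32 weeks) as primary independent variables" (38 is evidently a slip for 28). It also allows covariate-by-treatment interactions, lists weeks of gestation as a covariate, and carries the same approach into the Cox model.

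**The concern.** In Exploratory Aim 2 the objective covers all the timing arms, but the unadjusted analysis covers two. Followed literally, the ANOVA and Tukey steps give no estimate for the intermediate arm in either stratum. A third of the randomised mothers contribute nothing to them. Everywhere else, including Exploratory Aim 1, the plan compares three groups.

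In Exploratory Aim 1, chi-square cannot be run on a continuous percentage until someone groups it. With no grouping in the plan, the cut-points can be chosen once the data are visible. Grouping also discards information, and separate weekly tests ignore that the same infants are measured repeatedly.

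At stake is the usefulness and credibility of two exploratory results. The primary comparison does not depend on either.

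**Working it through.** **1. Counting the design**

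| Item | Available | In the ANOVA and Tukey steps |
|---|---|---|
| Timing-by-stratum cells | 3 x 2 = 6 | 2 x 2 = 4 |
| Mothers (60 per arm, Sample Size section) | 3 x 60 = 180 | 2 x 60 = 120 |
| Within-stratum timing contrasts | 3 x 2 = 6 | 1 x 2 = 2 |

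The count of 120 does not depend on how mothers divide between strata. It ignores dropout.

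**2. Reproducing the plan's own figure**

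Inputs from the Sample Size section: 60 per group, 34.1 hours, s = 55.0, two-sided alpha 0.02. Effect = 34.1/55.0 = 0.62 SD. Noncentrality = 0.62 x sqrt(60/2) = 3.396. Power is 0.858 by the normal approximation and 0.849 by the t distribution, against the stated 85%. The figure reproduces. The plan states no power for the exploratory aims.

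**3. What restoring the intermediate arm costs**

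Assumptions: 30 mothers per cell (even strata), familywise 0.05, no dropout, and a cross-sectional comparison of means. Effect 0.62 SD, so noncentrality = 0.62 x sqrt(30/2) = 2.401. The Tukey critical t is q/sqrt(2). Power is from the noncentral t.

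| Multiplicity family | df | Critical t | Early-late power in a stratum |
|---|---|---|---|
| Planned: Tukey over four cells | 116 | 2.607 | 0.42 |
| Tukey over all six cells (15 pairs) | 174 | 2.882 | 0.32 |
| Three timing contrasts per stratum, 0.025 per stratum | 174 | 2.631 | 0.41 |
| Same rule, early and late arms only | 116 | 2.271 | 0.55 |

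The first and third rows look equal, but two things change between them: an arm is added, and the between-stratum pairs leave the family. The fair comparison is the fourth row with the third: 0.553 - 0.411 = 0.142, or about 14 points.

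**4. Precision and the interaction**

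The 95% confidence interval half-width for early-late within a stratum at 30 per cell is about 1.97 x sqrt(2/30) = 0.51 SD, or 28 hours at s = 55. For the early-late-by-stratum interaction, SE = sqrt(4/30) = 0.365 SD and 0.62/0.365 = 1.698. Power at two-sided alpha 0.02 (the primary level; none is set for these aims) is about 0.26. An interaction test would therefore be weak.

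**5. Exploratory Aim 1**

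No arithmetic applies. The Statistical Analysis section pairs chi-square with categorical variables. Table 2 and the analysis section describe a weekly percentage. No passage turns one into the other.

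**The case against.** **The analysis is already available elsewhere.** The Aim 1 models include all three arms, allow covariate-by-treatment interactions and list weeks of gestation as a covariate. This stands in part. A reader might infer that the plan never looks at the intermediate arm by gestation, and the documents do not support that. What is missing is a named timing-by-stratum term, and any statement that those models serve Exploratory Aim 2.

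**The adjusted model may well include timing.** A reader might infer that the GLM drops timing, since gestational group is the only primary independent variable it names. That is not shown. The phrase about comparing adjusted means between the groups follows the list of four timing-by-stratum cells and most naturally refers to them. The wording is ambiguous, no more.

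**Two extreme arms may be a deliberate economy.** Section 3 of the working shows a real gain in power from restricting the family, so a reader should not infer that restoring the arm costs nothing. However, the plan does not give this as its reason. Nor can late be read as intermediate and late pooled, because Randomization fixes late at 181-360 minutes.

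**The power figures do not describe the models recommended.** This is correct. They concern a simple comparison of means, and a Cox model yields hazard ratios rather than hours. They show only the direction and rough size of the multiplicity cost.

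**Both aims are exploratory.** This stands, and it limits the weight of the point. It does not explain an unexplained omission or a test whose inputs are undefined.

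**Conclusion.** The point holds as a minor item on the exploratory aims. The Exploratory Aim 2 ANOVA and Tukey steps omit the intermediate arm without a reason (4 of 6 cells, about 120 of 180 mothers, 2 of 6 within-stratum timing contrasts). Exploratory Aim 1 assigns chi-square to a percentage with no categories. Both conclusions come from the text and the design count and rest on no power assumption. The power figures rest on even strata, familywise 0.05 and no dropout.

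Three smaller matters are missing detail rather than errors. Volume is taken over days 1-42 in the unadjusted step but days 1-7 in the adjusted one. The intake window is the first 6 weeks in Table 2 but the hospitalization in the analysis section. The unit of analysis for twins is not stated.

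A reader might infer that the primary analysis is compromised. It is not: the planned models for both primary outcomes use all three arms.

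**What to change.** **Exploratory Aim 2.** Add a timing (three levels) by gestational-stratum term to the mixed and Cox models already planned, or run the GLM on all six cells with timing named. Report the timing contrasts within each stratum with confidence intervals, with early-late as the lead contrast. Present the interaction as descriptive and say that its power is low. State the multiplicity family and the volume window. If the four-cell comparison is kept, state why the intermediate arm is left out and confirm that timing is in the adjusted model.

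**Exploratory Aim 1.** Replace chi-square with a mixed model for weekly percentage (arm, week, arm by week, stratum). If values pile up at 0 and 100%, use an ordinal model with categories fixed in advance. State the window and the unit of analysis. If the unit is the infant, allow for twins within mother.

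**Cost.** Revised analysis wording and somewhat more analysis work, with no new data and no change to the primary analysis. There are more contrasts to report, and adjusted early-late power is lower by about 14 points on the like-for-like rule above. That is a reasonable price when estimates with intervals are the main output of an exploratory aim.
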